4. ANALYSIS POPULATIONS

Population	Definition / Criteria	Analyses Evaluated
Intent-To-Treat	
 Comprise of all randomized subjects who receive at least one dose of study treatment and have a baseline assessment. This population will be analysed according to randomly assigned treatment 	
 Efficacy
Safety	
 Comprise of all enrolled subjects who receive at least one dose of study treatment. This population will be analysed according to the treatment the subject actually received. 	
 Safety
Per-Protocol	
 Comprise of all randomized subjects who complete study procedures through Week 26 and are compliant with the protocol. This population will be analysed according to randomly assigned treatment. Protocol deviations that would exclude subjects from the PP population are defined in Section 4.1 (Protocol Deviations) and Appendix 1 (Protocol Deviation Management and Definition for Per-Protocol Population). 	
 Supportive analyses of the efficacy endpoints
Pharmacokinetic	
 Subjects in the Safety population for whom a pharmacokinetic sample is obtained and analysed. 	
 PK

NOTES :

- Please refer to [Appendix 14](#) List of Data Displays which details the population to be used for each displays being generated.

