7.1.1.1. Primary Analysis on Primary Efficacy Endpoint

The primary endpoint is the change from baseline in HbA_{1c} at Week 26. The primary analysis of the primary endpoint will be conducted using a mixed-effect model with repeated measures (MMRM) in the ITT Population. The primary analysis will include all HbA_{1c} values collected at scheduled visits from Week 4 up to Week 26. This will include values after hyperglycemia rescue and discontinuation from investigational product. Imputation under the non-inferiority null hypothesis for missing data will be incorporated [Koch, 2008]. Multiple imputation assuming missing at random (MAR) will be used to replace missing data of change from baseline of HbA_{1c} at Week 26 for all subjects in both treatment arms as a first step, and then to make all the imputed values for the liquid drug product arm worse by the non-inferiority margin 0.4.

Multiple imputation approach under MAR uses separate means and variance-covariance parameter estimation for each treatment arm (Carpenter and Kenward, 2013). Missing values for each subject will be imputed multiple times based on his or her own observed HbA_{1c} change from baseline values available and also based on the estimated means and variance-covariance from the treatment group where that subject is randomized to. This approach will be used for all missing data at Week 26 due to any reason including, but not limited to lost to follow-up and withdrawal consent. The details of implementing this multiple imputation approach are the following:

- **Step 1a:** Missing values at Week 26 will be imputed 100 times via SAS PROC MI (specifying BY treatment group, using MCMC statement with the option chain = multiple, including baseline and all post-baseline scheduled visits up to Week 26). As a result, 100 imputed datasets will be generated. Note: Only imputed values at Week 26 will be retained while the imputed values at other visits will be dropped from the imputed datasets.
- **Step 1b:** For each of the 100 imputed datasets from Step 1 the imputed values at Week 26 for the liquid drug product arm will be increased by 0.4.
- **Step 2:** Apply MMRM analysis as specified below for each of the 100 imputed dataset and save LSmeans (standard error) for each treatment arm at Week 26 and difference in LSmeans between treatment groups (standard error) from each of the 100 analyses.

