11.6.3.4. Sensitivity Analysis Under Missing Not At Random (MNAR)

The impact of missing data will be explored, as outlined below, for the ITT Analysis Population only.

Examination of Missing Data Patterns

It is expected that the pattern of missing data will be similar in both treatment groups given the each treatment group is using the same drug but different formula.

To examine the nature of missing data, cohorts of subjects will be defined based on the scheduled assessments (HbA_{1c} change from baseline) that were completed at Weeks 1, 4, 8, 12, 16, 20, and 26.

- Subjects who have week 1 assessment only
- Subjects who have assessments up to and including Week 4 only
- Subjects who have assessments up to and including Week 8 only
- Subjects who have assessments up to and including Week 12 only
- Subjects who have assessments up to and including Week 16 only
- Subjects who have assessments up to and including Week 20 only
- Subjects who have assessments up to and including Week 26.

The number and percentage of subjects on each treatment in the 7 cohorts defined here will be tabulated. Graphical methods will be used to examine changes from baseline over time to assess the pattern of outcomes prior to withdrawal.

Sensitivity Analyses

The sensitivity of the results of analysis to the method of handling missing values will be investigated, especially if the number of missing values is substantial or if the characteristics of missing values differ between treatment groups.

To assess the impact of subjects who discontinued investigational product and stayed in the study; exclusion of data after treatment discontinuation may also be performed if a significant number of subjects discontinue study medication prior to Week 26. On treatment data will be analyzed using the same imputation/MMRM model as described in Section 7.1.1.1. The imputation will be performed for missing value at Week 26 due to any reason and also available value at Week 26, but off-treatment.

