Sensitivity analyses using a different type of multiple imputation method will be conducted. Firstly, missing data between two non-missing time points (i.e. intermittent missing data) will be considered missing at random (MAR). Secondly, missing data after the last available assessment due to any reasons (i.e. monotone missing data) will be imputed using last mean carried forward (LMCF), that is Missing Not At Random (MNAR) (Carpenter and Kenward, 2013). Thirdly, this approach assumes that a constant rate of increase in HbA_{1c} change from Baseline is experienced by subjects following withdrawal from the study. The imputed values based on LMCF will be then updated with an added delta using the following rates of HbA_{1c} increase: 0%/month, 0.1%/month, and 0.2%/month to explore the potential impact as in a tipping-point analysis. For each treatment group, these 3 rates will be assumed, resulting in 9 scenarios. The resulting treatment differences and associated P-values for non-inferiority will be tabulated against the varying rates of HbA_{1c} increase. This estimand is one where those who withdraw are assumed to revert to an unstable treatment regimen with an increasing rate of HbA_{1c}. For each imputation data set, an analysis of variance (ANCOVA) will be carried using Week 26 data, both actual and imputed, using the same covariates as in the primary analysis. Contrasts of interest will be estimated and then combined across

imputations using standard multiple imputation rules. The details of implementing this multiple imputation approach using delta method in combination with LMCF are the following:

- Step 1: Multiple Imputation under MAR ($K=100$ times)
 - Run PROC MI for all subjects BY treatment group (specifying the options chain=multiple in the MCMC statement).
 - As a result 100 sets of mean vectors (μ) and variance-covariance matrices (Σ) for each treatment group are simulated from the posterior distribution.
 - Each of the above 100 simulated parameter sets leads to a separate imputed dataset, in which the missing values (Y_2) for each subject are replaced by values drawn randomly from their conditional distribution given the observed values (Y_1). This condition distribution (Y_2/Y_1) is multinomial with mean $\mu_2 + \Sigma_{21} \Sigma_{11}^{-1} (Y_1 - \mu_1)$ and variance-covariance matrix $\Sigma_{22} - \Sigma_{21} \Sigma_{11}^{-1} \Sigma_{12}$. So, 100 imputed datasets are generated.

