- Step 2: Multiple Imputation using LMCF ($K=100$ times)
 - For each imputed dataset from Step 1, update the imputed values (post-last observation) as follows:
 - For each subject per treatment group, if there are any imputed values after the last observation (Y_p, imp), first split the simulated mean vector (μ) into three parts: μ_b (prior to last obs), μ_{last} (last obs) and μ_p (post last obs) and then update these imputed values as $Y^*_{p, \text{imp}} = (Y_p, \text{imp} - \mu_p + \mu_{\text{last}})$. Repeat for all subjects and for both treatment groups.
 - Repeat for the 100 imputed datasets from Step 1.
- Step 3: Multiple Imputation using Delta method ($K=100$ times)
 - Calculate delta value for each subject at each visit post-last observation
 - Let γ_1 and γ_2 be the rates of HbA1c increase per month after the last observation for the liquid and lyophilized treatment group, respectively.
 - Let τ be the length of time between visits. Also, consider 1 month=4 weeks and determine τ using the visit week values. For example, time between visits Week 16 and Week 20 is 4 weeks (i.e. 1 month) and time between visits Week 16 and Week 26 is 10 weeks (i.e. 10/4=2.5 months).
 - For each subject and each visit post-last observation, a delta value will be derived according to the treatment group the subject was randomized to and time between the last observation visit and the present visit (τ). If the subject belongs to the liquid treatment group, the delta value = $\gamma_1 \times \tau/4$; if the subject belongs to the lyophilized treatment group, the delta value = $\gamma_2 \times \tau/4$.
 - For each updated imputed dataset from Step 2 increase the imputed values post-last observation by the corresponding delta values (per subject per visit post-last observation).
 - Repeat for the 100 imputed datasets from Step 2

- Step 4: Repeat Step 1, Step 2 and Step 3 for 9 scenarios based on 3 different rates of HbA1c increase for each treatment group (i.e. $\gamma_1, \gamma_2=0/\text{month}$, $0.1/\text{month}$ and $0.2/\text{month}$)
- Step 5: For each scenario, apply ANCOVA analysis at Week 26 for each of the 100 imputed dataset and save the difference in LSmeans between treatment group and the associated standard error from each of the 100 analyses.

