11.11. Appendix 11: Model Checking and Diagnostics for Statistical Analyses

11.11.1. Model Checking and Diagnostics for Statistical Analyses

1. Example SAS code for the primary efficacy analysis with imputation

Step 1a: Transpose the data horizontally and then impute data assuming missing at random (EFFIM)

```
PROC MI DATA= EFF OUT= EFFIM NIMPUTE=100 SEED=4408572;
  BY TRT01PN;
  MCMC CHAIN=multiple;
  VAR BASE CHG_W1 CHG_W4 CHG_W8 CHG_W12 CHG_W16 CHG_W20 CHG_W26;
  RUN;
```

Note: need to remove all imputed values before Week 26 and retain imputed values at Week 26 only.

Step 1b: Add 0.4 to the imputed value at Week 26 in the liquid product arm and transpose data in vertical structure (EFFIM2)

Step 2: Exclude HbA1c change from baseline at Week 1 and perform MMRM for each imputed dataset

```
Ods output SLICES=SLICE LSM SLICEDIFFS=SLICEDIFF;
```

```
PROC MIXED DATA= EFFIM ;
  BY _imputation_;
  CLASS USUBJID REGION WGTGR1 AGEGR1 PRIORDTX TRT01PN AVISITN;
  MODEL CHG= BASE REGION WGTGR1 AGEGR1 PRIORDTX TRT01PN AVISITN
  TRT01PN*AVISITN BASE*AVISITN/ DDFM=KR;
  REPEATED AVISITN/SUB=USUBJID TYPE=UN;
  SLICE TRT01PN*AVISITN/sliceby(AVISITN='26') means pdiff cl cov;
  RUN;
```

Step 3: Combine results using PROC MIANALYZE

```
PROC SORT DATA=SLICE LSM; BY TRT01PN IMPUTATION; RUN;
PROC MIANALYZE DATA=SLICE LSM EDF=CDF*;
BY TRT01PN;
MODELEFFECTS ESTIMATE;
STDERR STDERR;
RUN;
```

```
PROC MIANALYZE DATA=SLICEDIFF;
MODELEFFECTS ESTIMATE;
STDERR STDERR;
RUN;
```

*CDF=complete-data degrees of freedom. This is used to calculate the adjusted degrees of freedom for the combined results.

2. Example SAS code for the by-subgroup analysis of the primary endpoint with imputation

Follow the same steps as for the example SAS code for the primary analysis except in the step 2 additional interaction terms need to be added.

Subgroup variable: Baseline HbA1c <8% or >=8%

```
ods output SLICES=SLICELSM1 SLICEDIFFS=SLICEDIFF1;
PROC MIXED DATA= EFFIM;
  BY imputation;
  CLASS USUBJID REGION WGTGR1 AGEGR1 PRIORDTX TRT01PN AVISITN HBGR1;
  MODEL CHG= HBGR1 REGION WGTGR1 AGEGR1 PRIORDTX TRT01PN AVISITN
TRT01PN*AVISITN HBGR1*TRT01PN HBGR1*AVISITN
          HBGR1*TRT01PN*AVISITN/ DDFM=KR;
  REPEATED AVISITN/SUB=USUBJID TYPE=UN;
  SLICE HBGR1*TRT01PN*AVISITN/sliceby(AVISITN='26') means pdiff cl
cov;
RUN;
```

Subgroup variable: Baseline Weight <90 or >=90 kg

```
ods output SLICES=SLICELSM2 SLICEDIFFS=SLICEDIFF2;
PROC MIXED DATA= EFFIM;
  BY imputation;

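### The last-mean-carried-forward sensitivity analysis has no valid last mean for ITT subjects whose only HbA1c is baseline

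*SAP*

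**What the plan says.** **Who is included.** SAP section 4 defines ITT as "all randomized subjects who receive at least one dose of study treatment and have a baseline assessment". No post-baseline HbA1c is needed. SAP 11.6.3.4 applies the missing-data analyses to the ITT population.

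**LMCF Step 1.** The instruction is "Run PROC MI for all subjects BY treatment group (specifying the options chain=multiple in the MCMC statement"). No variables are listed.

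**LMCF Step 2.** For each subject, "if there are any imputed values after the last observation", the plan is to "first split the simulated mean vector" into parts before, at and after the last observation. Each later imputed value then has its own visit mean subtracted and the last-observation mean added. Nothing requires the last observation to be post-baseline.

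**LMCF Step 3.** A delta of 0, 0.1 or 0.2 per month is added, counted from the last observation visit.

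**The only variable list.** SAP 7.1.1.1 describes the primary imputation as "including baseline and all post-baseline scheduled visits up to Week 26", and the example code in SAP 11.11.1 reads "VAR BASE CHG_W1 CHG_W4 CHG_W8 CHG_W12 CHG_W16 CHG_W20 CHG_W26". The first element is an HbA1c level; the others are changes.

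**Missing-pattern table.** The seven cohorts start with "Subjects who have week 1 assessment only".

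**The concern.** LMCF assumes that, after dropping out, a subject stays at the mean of the last visit seen. That works only if every element of the mean vector is on the same scale. A subject with baseline alone is the exception: the last mean is either a level of 7 to 10 added to a change score, or it does not exist. In the first case the subject is imputed a Week 26 HbA1c of about 16%, and the value enters the ANCOVA in all nine delta scenarios.

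This is the tipping-point analysis (Table 2.19) meant to show that the non-inferiority result survives informative dropout. An artefact from one or two subjects could weaken or flatter it for reasons unrelated to the formulations, and a repair after unblinding would look driven by the data. Because the cohort table has no row for these subjects, it would not show how many there are.

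**Working it through.** **Planning figures.** The LMCF section states no figure of its own. The sample size reproduces: margin 0.4, SD 1, one-sided 0.025 and 133 per arm give 90.1% power by the noncentral t. Allowing for 13% dropout, 133/0.87 = 152.9, against about 150 planned.

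**What Step 2 does to a baseline-only subject.** The rule is Y* = Y_imp − mu_p + mu_last. Averaged over draws and over such subjects, Y_imp is about mu_p, so the expected Y* is mu_last.

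| Content of the vector | mu_last | Expected imputed Week 26 change |
|---|---|---|
| Baseline level plus change scores (the only list in the SAP) | mean baseline HbA1c | +7 to +10; +8.2 if the mean is 8.2 |
| Change scores only | does not exist | undefined |
| Absolute HbA1c at every visit | mean baseline level | about 0 once converted to a change |

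The 7 to 10 range is the eligibility range; the documents give no baseline mean. The third reading is harmless, but nothing in the SAP specifies it. The LMCF text speaks of a rise in change from baseline, and the code uses change variables.

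**Size under the first reading.** Assumptions: 150 per arm, mean baseline 8.2, mean Week 26 change −0.9, SD 1.0, baseline-change correlation −0.3, true difference 0.

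- Displacement from a missing-at-random value: 8.2 + 0.9 = 9.1. Arm mean shift: 9.1/150 = 0.061.
- Excess over a last mean of 0: 8.2/150 = 0.055. For baseline means of 7 to 10 this is 0.047 to 0.067.
- Residual variance with nobody affected: 1 − 0.3² = 0.91. SE = √(0.91 × 2/150) = 0.110.
- With one affected subject: 0.91 + 9.1² × (149/150)/297 = 1.187. SE = √(1.187 × 2/150) = 0.126.

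The chance that the upper bound is at most 0.4, with critical value 1.968 and sampling SD 0.110:

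- Nobody affected: Φ((0.4 − 1.968 × 0.110)/0.110) = 95%.
- One in the liquid arm: Φ((0.4 − 0.061 − 1.968 × 0.126)/0.110) = 80%.
- One in the lyophilized arm: Φ((0.4 + 0.061 − 1.968 × 0.126)/0.110) = 97%, with the point estimate moved 0.061 in favour of liquid.

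The starting value is 95% rather than 90% because this calculation uses 150 per arm and an ANCOVA residual SD of 0.954.

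**Simulation checks.** Two separate simulations with Rubin pooling agree with the formula. With mean baseline 8.2, one liquid-arm subject gave 79% (SE 0.126). With mean baseline 8.0 and change −0.8, the results were:

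| Baseline-only subjects (liquid, lyophilized) | Baseline level used as last mean | Last mean set to 0 |
|---|---|---|
| 0, 0 | 95% | 95% |
| 1, 0 | 80% | 94% |
| 1, 1 | 85% | 95% |
| 3, 0 | 23% | 94% |

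Even a balanced pair costs power, because the two outliers inflate the SE (0.138 against 0.111).

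**Step 3.** If these subjects' delta is counted from Week 0, it is 26/4 = 6.5 months, or 0, 0.65 and 1.3 at the three rates. The SAP does not say so for a subject with no post-baseline visit.

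**Cohorts.** A baseline-only ITT subject fits none of the seven, so with any such subject the table does not sum to ITT. This holds under every reading.

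**The case against.** The strongest reply is that the +8 rests on an inference. The variable list with baseline in front belongs to the primary analysis, and the SAP introduces LMCF as a different type of imputation without repeating the list. The same section describes the scheduled assessments as changes at Weeks 1 to 26, which suggests that baseline is not an observation in the series. This stands: +8 is conditional. It does not rescue the step, because the change-only reading leaves the last mean undefined.

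The second reply is that there may be no such subjects. HbA1c is drawn at Week 1; any record on days 2 to 18 is slotted there, including unscheduled and early-withdrawal records. Subjects who stop treatment stay in the study, and those who withdraw are asked to complete the end-of-treatment assessments. This also stands: the number is unknown and probably small. But 13% withdrawal is planned for, about 20 per arm (0.13 × 150 = 19.5), and one subject leaving before any further sample is enough.

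Third, the primary analysis uses a missing-at-random draw plus 0.4 and does not involve Step 2, and the nine scenarios carry no decision rule. Both are correct and limit the consequence to the credibility of the sensitivity analysis.

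A reader might infer that the algorithm is certain to impute +8, that early dropouts would drive the result, or that all nine scenarios would fail. The documents support none of these: the LMCF vector is unstated, no count is given, and with one affected liquid-arm subject and no added delta the margin would still be met about four times in five.

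**Conclusion.** The gap is real. Step 2 gives no valid last mean for ITT subjects with baseline only, under either reading that has support in the text. If the SAP's only variable list is reused, the imputed change is about +8 (7 to 10), each unbalanced subject moves its arm mean by about 0.055 relative to a last mean of 0, and one liquid-arm subject lowers the chance of meeting the margin from about 95% to about 80%. One in the lyophilized arm biases the other way.

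These sizes depend on the assumed mean baseline (8.2), Week 26 change, SD and correlation, 150 per arm and a true difference of 0. For baseline means of 7 and 10, with a change of −0.8, the 80% becomes about 84% and 73%. The point should be settled before unblinding, but it concerns one sensitivity analysis and probably few subjects. It does not touch the primary result.

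**What to change.** In SAP 11.6.3.4:

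1. Step 1: state the PROC MI variable list and the outcome scale for the LMCF analysis.
2. Step 2: restrict the last mean to the change scale, and set it to 0 when baseline is the only observation.
3. Step 3: count the delta from Week 0 for these subjects.
4. Missing-pattern table: add an eighth cohort with no post-baseline assessment, so that these ITT subjects are counted.

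Retaining the missing-at-random draw for these subjects would be another workable rule for item 2, but 0 is closer to the LMCF idea. The cost is a few clarifying sentences, one table row and a line of code. No new data are needed and the primary analysis does not change.

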11.6.3.5. Sensitivity Analysis for Potential Data Fabrication

In case where there are data integrity issues, that would impact the outcome of the trial results, we may perform a sensitivity analysis by excluding certain sites from the primary analysis.

11.7. Appendix 7: Values of Potential Clinical Importance

11.7.1. Laboratory

Hematology			
Laboratory Test	Units	Change from Baseline of Potential Clinical Concern	Potential Clinical Concern Value
Basophils	GI/L	None	None
Eosinophils	GI/L	None	None
Hematocrit	1	>0.1 decrease	>0.05 below LLN >0.04 above ULN
Hemoglobin	g/L	>25 g/L decrease	>20 g/L below LLN >10 g/L above ULN
Lymphocytes	GI/L	None	<0.5 x LLN
Monocytes	GI/L	None	None
Neutrophils	GI/L	None	<1 GI/L
Neutrophil Bands	GI/L	None	None
Platelets	GI/L	None	<80 GI/L >500 GI/L
Red Blood Cell Count	TI/L	None	None
Segmented Neutrophils	GI/L	None	<0.5 x LLN
White Blood Cell Count	GI/L	None	>1 GI/L below LLN >5 GI/L above ULN

Chemistry			
Laboratory Test	Units	Change from Baseline of Potential Clinical Concern	Potential Clinical Concern Value
Albumin	g/L	None	>5 g/L above ULN or below LLN
Alkaline Phosphatase	U/L	None	>3 x ULN
ALT	U/L	None	>3 x ULN
AST	U/L	None	>3 x ULN
Bicarbonate (Carbon Dioxide Content)	mmol/L	None	<16 mmol/L > 40 mmol/L
Blood Urea Nitrogen	mmol/L	None	>2 x ULN
Calcitonin	pmol/L	None	>100

Chemistry			
Laboratory Test	Units	Change from Baseline of Potential Clinical Concern	Potential Clinical Concern Value
Calcium	mmol/L	None	<1.8 mmol/L >3.0 mmol/L
Chloride	mmol/L	None	None
Creatinine	umol/L	None	>159 umol/L
Direct Bilirubin	umol/L	None	>1.35 x ULN
Gamma Glutamyl Transferase	U/L	None	>3 x ULN
Glucose (fasting)	mmol/L	None	<3 mmol/L >22 mmol/L
Potassium	mmol/L	None	>0.5 mmol/L below LLN >1.0 mmol/L above ULN
Sodium	mmol/L	None	>5 mmol/L above ULN or below LLN
Total Bilirubin	umol/L	None	>1.5 x ULN
Total Protein	g/L	None	>15 g/L above ULN or below LLN
Uric acid	umol/L	None	>654 umol/L
Free Fatty Acids	mmol/L	None	None
HDL Cholesterol	mmol/L	None	None
LDL Cholesterol	mmol/L	None	None
Triglycerides	mmol/L	None	> 9.04 mmol/L
Total Cholesterol	mmol/L	None	None

Liver Function Tests

Liver Function Tests	
Laboratory Test	Potential Clinical Concern Value
ALT	≥ 2 x ULN ≥ 3 x ULN ≥ 5 x ULN ≥ 8 x ULN ≥ 10 x ULN ≥ 3 x ULN and Total Bilirubin ≥ 2 x ULN
AST	≥ 2 x ULN ≥ 3 x ULN ≥ 5 x ULN ≥ 8 x ULN ≥ 10 x ULN ≥ 3 x ULN and Total Bilirubin ≥ 2 x ULN
Total Bilirubin	≥ 1.5 x ULN ≥ 2 x ULN ≥ 3 x ULN ≥ 5 x ULN ≥ 8 x ULN ≥ 10 x ULN

11.7.2. Vital Signs

Parameter	Units	Change from Baseline of Potential Clinical Concern	Potential Clinical Concern Value
Systolic BP	mmHg	Decrease >30 mmHg Increase >30 mmHg	<100 mmHg >170 mmHg
Diastolic BP	mmHg	Decrease >30 mmHg Increase >30 mmHg	<50 mmHg >110 mmHg
Heart rate	bpm	Decrease >30 bpm Increase >30 bpm	<50 bpm > 120 bpm

